The definition has been simplified to allow for the capture of PJI through databases and registries without review of medical files and the modifications are expected only to give minor non-significant changes for the capture of PJI (34, 36). Data will be extracted from DNRP, DHR, MiBA and HAIBA. Positive culture samples (aspirations, tissue biopsies or fluid) must be obtained from the relevant hip joint. As part of standard care, a sample of at least 5 tissue biopsies are obtained at revision surgery. All samples are sent for microbiological analysis at one of ten regional departments of clinical microbiology who have standardized methods for handling of biopsies and culturing. The cumulative proportion of patients remaining PJI-free in the two groups will be presented as illustrated in Mockup Figure 2.

Key secondary endpoints evaluated within 90 days from primary THA

1) Serious Adverse Events (SAEs)

Number of patients with one or more SAEs. SAEs are defined according to the guidelines provided by the International Council for Harmonization of Technical Requirements for Human Use (ICH-GCP) (39). SAE refers to an event involving a significant risk of death or disability of the patient (or their offspring), including, but not limited to, an event that: (1) results in death, (2) is life-threatening – in the investigator's opinion the patient was in immediate risk of death from the adverse event when it appeared, (3) requires hospitalization or prolongs existing hospitalization (4) results in permanent or significant disability. SAEs are recorded from DNPR. The list of ICD10 codes to identify SAEs is listed in Appendix C. This list has been curated to include diagnoses that are considered clinically significant, potentially life-threatening, requiring hospitalization, or resulting in persistent or significant disability/incapacity. To ensure comprehensive coverage and adherence to international standards, any additional codes that meet the criteria for SAEs as defined by the ICH-GCP guidelines will also be included.

2) Potential PJI referred to as *PJI-likely*

Incidence of potential PJI. PJI-likely is defined as at least one of the two criteria is fulfilled:

A: One single intraoperatively obtained positive culture obtained from reoperation (aspiration fluid OR tissue biopsy) regardless of microorganism

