B: One single positive culture obtained from aspiration of synovial fluid regardless of microorganism AND any antibiotic prescriptions (ATC category J01) redeemed

These definitions of PJI-likely are based on a modified version of EBJIS (33) as described previously (see primary outcome) and the study by Milandt *et al.* (40) where first-time revisions with one positive culture were found to have a higher risk of re-revision for PJI.

Cases of PJI-likely, will be captured in HAIBA and MIBA, and registration of antibiotic prescription in NPR. Positive culture samples (aspirations, tissue biopsies or fluid) must be obtained from the relevant hip joint.

3) Length of stay for hospitalization (LOS)

Length of hospital stay (continuous measure [days]) is defined as number of postoperative overnight stays, including transfers to other departments and hospitals within 24 hours. Data on LOS is acquired from DNPR.

4) Major Adverse Cardiovascular Events

Incidence of Major Adverse Cardiovascular Events (MACE). A MACE is defined a priori to include thromboembolic complications including venous thromboembolism, myocardial infarction, atrial fibrillation and stroke based on the diagnostic ICD10 codes listed in Appendix B. VTE is defined a priori as both deep venous thromboembolisms confirmed by compression ultrasound and pulmonary embolism confirmed by spiral computed tomography (CT), ventilation-perfusion scintigraphy or pathological removal of an embolus and based on the following diagnostic ICD10 codes: I26, I80.1-I80.9, I82.1-I82.9, or T81.7B-D. Data will be extracted from DNPR.

5) Hospital-treated infections (Other than those listed above)

Patients with at least one hospital-treated infection are defined as those with first-time hospital admission for a primary or secondary infection diagnosis following discharge from the index THA surgery. Hospital-treated infections are identified from DNPR based on ICD-10 codes listed in Appendix B. The list of infections includes chronic and more rare infections, to detect possible flare-ups in any possible ongoing infections. This outcome does not include infections treated during index admission for arthroplasty surgery.

6) Community-based antibiotic use

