Opioid use	The Danish National Prescription Registry (NPR)	Following ATC codes (including all subcodes) are included: N01AH (opioid anesthetics), N02A (opioids), N07BC02 (methadone), and R05DA04 (codeine).
Use of acetaminophen or non-steroidal anti-inflammatory drugs	The Danish National Prescription Registry (NPR)	Acetaminophen ATC codes: N02BE01 and N02BE51 Non-steroidal anti-inflammatory drug ATC codes: M01A
Any revision after THA	Danish Hip Arthroplasty Registry (DHR) and The Danish National Patient Registry (DNPR)	Code for revision for infection in DHR: DHR: Variable 2: "Revision"

Appendix C: International Classification of Diseases, 10th Revision Diagnosis Codes for Serious Adverse Events

Serious Adverse Event	ICD-10 Diagnostic Code
Sepsis	A40 - A41
Shock not elsewhere classifies R67	R67
Anaphylactic Shock, unspecified	T78.2

Other types of shock included in codes below	
 • anesthesia (T88.2) • anaphylactic (due to): 
 ◦ serum (T80.5) • postoperative (T81.1) • traumatic (T79.4)
Staphylococcal scalded skin syndrome	L00
Infectious arthropathies	M00-M03
Osteomyelitis	M86
Injuries to the hip and thigh	S70-S79
Poisoning by drugs, medicaments and biological substances	T36 – T50
Certain early complications of trauma, not elsewhere classified	T79
Complications of surgical and medical care, not elsewhere classified	T80 – T88
Pneumothorax	J93
Respiratory failure, not elsewhere classified	J96
Postprocedural respiratory disorders, not elsewhere classified	J95
Adult respiratory distress syndrome	J80
Pulmonary oedema	J81
Cardiac arrest	I46

Other forms of heart disease	I30 – I52
Ischemic heart diseases	I20 – I25
Acute and subacute endocarditis	I33
Acute myocarditis	I40
Heart failure	I50
Complications and ill-defined descriptions of heart disease	I51
Pulmonary heart disease and diseases of pulmonary circulation	I26-I28
Arterial embolism and thrombosis	I74
Phlebitis and thrombophlebitis	I80
Portal vein thrombosis	I81
Other venous embolism and thrombosis	I82
Intracranial and intraspinal phlebitis and thrombophlebitis	G08
Postprocedural disorder of circulatory system, unspecified	I97.9
Acute kidney failure	N17
Type 1 diabetes mellitus with diabetic ketoacidosis	E10.1

Type 2 diabetes mellitus with diabetic ketoacidosis	E11.1
Other specified diabetes mellitus with diabetic ketoacidosis	E13.1
Stroke	I60-I64
External causes of morbidity and mortality	Y40 – Y84
Acute appendicitis	K35
Acute peritonitis	K65

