Perforation of intestine	K63.1
Abscess (perianal, ischiorectal, intraspincteric)	K61
Hemoperitoneum	K66.1
Other and unspecified intestinal obstruction	K56.6
Ileus	K56
Hematemesis	K92.0
Melena	92.1
Gastrointestinal hemorrhage unspecified	92.2
Acute Pancreatitis	K85
Cholangitis	83.0
Acute cholecystitis	K81.0
Perforation of gallbladder	K82.2
Abscess of liver	K75.0

Perforation of the esophagus	K22.3
Gastric ulcers with bleeding or perforation	K25.0 to K25.6
Duodenal ulcers with bleeding or perforation	K26.0 to K26.6
Gastrojejunal ulcers with bleeding or perforation	K28.0 to K28.6
Diverticular disease with perforation, abscess, or bleeding	K57.0, K57.2, K 57.4, K57.8
Diaphragmatic hernia with obstruction or gangrene	K44.0, K44.1
Peritonitis	K65
Abscess of intestine	K63.0
Perforation of intestine	K63.1 (non traumatic)

Serious Adverse Event	ICD-10 Diagnostic Code
Surgical site infection	T81.40, T81.41, T81.42, T81.43, T81.49
Venous thromboembolism	I26, I80, T81.7B
Cardiac Arrest	I46, I97.12
Acute myocardial Infarction	I21
Stroke	I60 - I64
Pancreatitis	K85

Pneumonia	J13, J14, J15, J16, J17, J18, J85.1, T81-4P
Acute kidney injury	N17
Wound dehiscence	T81.3

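### Serious adverse events are found by matching Appendix C codes with no rule on contact type or new admission, so long-standing heart disease can count as an event; the code list is also not fixed

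*SAP*

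**What the plan says.** SAEs are the first of the key secondary endpoints in the SAP and the outcome compared under Harms. The measure is binary per patient: "Number of patients with one or more SAEs", under the heading "Key secondary endpoints evaluated within 90 days from primary THA". The concept follows ICH-GCP, and one of its criteria is that the event "requires hospitalization or prolongs existing hospitalization".

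Identification works differently: "SAEs are recorded from DNPR. The list of ICD10 codes to identify SAEs is listed in Appendix C". The same paragraph adds that "any additional codes that meet the criteria for SAEs as defined by the ICH-GCP guidelines will also be included".

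The first table of Appendix C mixes acute diagnoses with whole ICD-10 blocks, among them ischaemic heart disease (I20-I25) and "Other forms of heart disease" (I30-I52). A second, shorter table follows with different code sets for some of the same events. The SAE row of Appendix B refers to an appendix numbered XX, and names the Civil Registration System as the source for date of death.

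Hospital-treated infections (key secondary endpoint 5) come from the same registry, but a patient qualifies only through a "first-time hospital admission for a primary or secondary infection diagnosis following discharge from the index THA surgery", and infections treated during the index admission are left out.

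**The concern.** The definition and the extraction rule do not describe the same set of patients. The definition requires a serious event. The rule, as far as it is written down, requires a code from a list that includes long-standing conditions. A patient with known atrial fibrillation or stable ischaemic heart disease could be counted because the diagnosis was recorded at an outpatient visit, or as a secondary diagnosis of the index stay, without any new event.

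Such matches reflect comorbidity and not the antibiotic regimen, so they should be about equally frequent in both arms. They add noise and pull the comparison towards no difference. A null SAE result could then be read as reassurance when part of it is coding background. Because the list is also not settled, two analysts following this SAP could produce different SAE counts.

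**Working it through.** **1. Concept against rule.** The SAP text sets these conditions on the two endpoints taken from DNPR:

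| Condition | SAEs (endpoint 1) | Hospital-treated infections (endpoint 5) |
|---|---|---|
| Code list | Appendix C, extendable | Appendix B |
| Admission required in extraction | not stated | yes, first-time admission |
| After index discharge | not stated | yes |
| Index stay | not stated | excluded |
| Diagnosis position | not stated | primary or secondary |

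The SAP's account of the Charlson index shows that DNPR holds primary and secondary diagnoses from both hospitalisations and outpatient visits. That passage concerns the look-back before surgery. It shows what the registry contains, not which contacts the SAE query will use.

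**2. What the blocks contain.** Appendix B codes atrial fibrillation as I48.0 to I48.92, which lies inside I30-I52. The separate Appendix C rows for I33, I40, I46, I50 and I51 add nothing, since the same block already contains them.

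**3. Two tables.** In the first table of Appendix C the entry that covers myocardial infarction is I20-I25. In the second it is I21 only. Venous thromboembolism is I26, I80 and T81.7B in the second, while the first has I26-I28, I80, I81 and I82. Pneumonia appears only in the second. Nothing says whether one table governs or the two are to be combined.

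**4. Size of the dilution.** The SAP states no SAE rate, effect or precision, so there is no figure of its own to reproduce. Let p be the risk of a true new SAE, and b the share with a background code, equal in both arms and independent of treatment. Then:

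- observed risk q = 1 - (1 - p)(1 - b)
- observed risk difference = (1 - b)(p1 - p0)
- power = Φ(RD/SE - 1.96), with SE = √[(q0(1 - q0) + q1(1 - q1))/n]

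Inputs: n = 10,000 per arm (SAP, Sample size) and two-sided 5%. Assumed: p0 = 5% (multiple dose), p1 = 6% (single dose), and the values of b. Clustering is ignored.

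| b | q0 | q1 | RR | OR | RD (points) | Power |
|---|---|---|---|---|---|---|
| 0 | 5.00% | 6.00% | 1.200 | 1.213 | 1.00 | 87% |
| 5% | 9.75% | 10.70% | 1.097 | 1.109 | 0.95 | 60% |
| 10% | 14.50% | 15.40% | 1.062 | 1.073 | 0.90 | 43% |
| 15% | 19.25% | 20.10% | 1.044 | 1.055 | 0.85 | 33% |
| 20% | 24.00% | 24.80% | 1.033 | 1.044 | 0.80 | 26% |

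With the same true RR of 1.20 and b = 0, 5%, 10% and 20%, power is 66%, 31%, 21% and 13% if p0 is 3%, and 98%, 89%, 76% and 53% if p0 is 8%.

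**5. Direction.** Swap the arms, so that single dose has 5% and multiple dose 6%. The true RR is 0.05/0.06 = 0.833. At b = 10% the observed RR is 0.145/0.154 = 0.942. The pull is towards 1 in both directions.

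**The case against.** The SAP never says that every code match is an SAE. It defines the concept by ICH-GCP and offers Appendix C as a means of identification, so a sensible analyst might restrict the query to admissions. It is therefore too strong to say that stable disease will be counted; the documents support only that it can be. That still leaves a defect, because the restriction is written for infections and absent here.

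Several stronger readings are tempting and do not hold:

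- A reader might infer that the dilution favours a non-inferiority conclusion. The 1.4 margin applies to the primary endpoint only, SAEs have no non-inferiority test, and key secondary endpoints are to be interpreted with caution. The SAP's introduction mentions systemic toxicity after prolonged antibiotic use, so dilution could equally hide an advantage of the single dose.
- A reader might judge the loss by the RR alone. The Harms section also names the risk difference, which shrinks far less.
- A reader might infer that the list could be tuned to the results. Additions are limited to codes that meet ICH-GCP criteria, the statistical analyst is blinded, and two interpretations are signed before the code is unsealed. These safeguards lessen the risk. What remains is that no lock date is stated.
- A reader might treat every broad block as chronic disease. Y40-Y84 is labelled as external causes and is not an example.
- A reader might infer that events will be lost through entries printed without a letter (92.1, 92.2, 83.0). For instance, "Gastrointestinal hemorrhage unspecified" carries 92.2 two rows below K92.0. These are clerical slips, possibly from PDF reading, and are easily corrected.

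Safety also does not rest on the composite alone. Table 3 lists pulmonary embolism, deep venous thrombosis, myocardial infarction, stroke and death separately, and MACE and hospital-treated infections are endpoints of their own.

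**Conclusion.** The point holds for the extraction rule and for the unsettled list. The SAP defines SAEs by seriousness but gives a code match without a contact or admission condition, over blocks that take in long-standing heart disease. Two differing Appendix C tables and an extension clause with no cut-off leave the endpoint open.

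The direction of the effect follows from the definition if background coding is equal in the arms: ratios move towards 1 and the risk difference is multiplied by (1-b). Its size cannot be derived from the SAP, since neither p nor b is given. The figures above, such as RR 1.20 falling to 1.06 and the risk difference falling from 1.00 to 0.90 points at b = 10%, are illustrations under stated assumptions. They do not show a bias towards either regimen. This concerns a key secondary safety endpoint, leaves the primary analysis untouched, and should be settled before unblinding.

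**What to change.** - Count an Appendix C code only when it is a diagnosis of a new acute inpatient admission after index discharge and within 90 days, or a newly recorded diagnosis during the index stay that prolongs it. Say how prolongation is to be read from the registry. Add death from the Civil Registration System, as Appendix B already lists.
- Do not exclude an acute admission because the same diagnosis appears in the look-back. An admission for worsening of known heart disease is an SAE under the SAP's own definition.
- State one governing Appendix C list, resolve the two tables, and replace the XX reference in Appendix B.
- Lock the list before unblinding, and preferably before extraction. Put any later code in a labelled sensitivity analysis only.
- Correct the letterless codes, and the T81-4P entry in the pneumonia row, as a clerical matter.

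The cost is SAP wording and a filter on contact type and date in the DNPR extraction. The downside is that some SAEs managed wholly as outpatients are no longer counted.

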Community-based antibiotic use (any community-treated infection or antibiotic use after discharge) is defined as at least one dispensing after discharge from index THA surgery and broad-spectrum antibiotics based on the Anatomical Therapeutic Chemical classification (ATC) codes. All antibiotics in Denmark require prescriptions from a physician. The Danish National Health Service Prescription Database has registered all reimbursed prescriptions from all community pharmacies since 2004. Medications are coded according to the ATC codes listed in Appendix B. All antibiotics in Denmark require prescriptions from a physician and these will be identified using NPR (41). We aim to specifically examine the redemption of ATC code J01E prescriptions within one week following the index operation to capture instances of post-operative urinary tract infections.

7) Opioid use

Patients who received at least one opioid prescription following primary THA surgery. All opioids in Denmark require prescriptions from a physician and these will be identified using NPR (41). The following ATC codes (including all subcodes) are included: N01AH (opioid anesthetics), N02A (opioids), N07BC02 (methadone), and R05DA04 (codeine). Given the lack of a clear definition for opioid users, we defined opioid users as patients who redeemed two opioid prescriptions within six months prior to THA surgery. Conversely, patients who did not redeem two or more opioid prescriptions within this timeframe were classified as opioid naïve. For opioid naïve patients, opioid use post-THA is defined as the redemption of two opioid prescriptions within 90 days following surgery. We assert that two separate redeemed prescriptions confirm actual medication use. We will calculate the treatment dosage based on the number of packages and volume redeemed within 90 days post-surgery. To investigate dosages, all doses will be converted to morphine milligram equivalents using a conversion factor specific to the type of opioid (42, 43).

8) Use of acetaminophen or non-steroidal anti-inflammatory drugs

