Appendix A: Flow diagram illustrating dataset construction, including codes where applicable.

Appendix B: Registries, codes, and variables for each outcome

Outcome	Registry	Codes for Registry
Primary Outcome: Prosthetic Joint infection	Danish Hip Arthroplasty Registry (DHR) The Hospital Acquired Infections Database (HAIBA) The Danish Microbiological Database (MiBa)	Code for revision for infection in DHR: DHR: Variable 2: "Revision" HAIBA: Variable "SSI_acute_90 = 0 OR 1", 0 = infection that occurred between 3 and 90 days after a planned index operation. 1 = infection that occurred between 3 and 90 days after an acute index operation. MiBA: "Prøvedato"=corresponding to date or revision, "Resultat"=positive for microorganism, "Prøvemateriale"=closed fluid aspirate taken intraoperatively, "Konklusion på undersøgelse" or "Dyrkningsfund" = phenotypically indistinguishable from bacteria found in tissue biopsy
Serious Adverse Events	The Danish National Patient Registry (DNPR) The Civil Registration System	Please see Appendix XX for the complete outline of ICD-10 codes. The civilregistration system: variable: date of death
PJI-likely	The Danish Microbiological	MiBA: "Prøvedato"= between 3 and 90 days after a planned index operation , "Resultat"=positive for microorganism, "Prøvemateriale"=aspiration of synovial fluid OR closed fluid aspirate taken

	Database (MiBa) The Danish National Prescription Registry (NPR)	intraoperatively, "Lokation" = corresponding to THA from index surgery "Undersøgelse" = aspiration with or without imaging guidance or biopsy "Konklusion på undersøgelse" or "Dyrkningsfund" = phenotypically indistinguishable from bacteria found in tissue biopsy From the prescription database (NPR): (ATC category J01
Length of stay for hospitalization	The Danish National Patient Registry (DNPR)	From date of index surgery to date of discharge.
Major Adverse Cardiovascular Events	The Danish National Patient Registry (DNPR)	The following ICD.10 codes: Venous thromboembolism: I26, I80.1 –I80.9, I82 or T81.7 Myocardial infarction: I20 – I25 Atrial fibrillation: I48.0 -I48.92 Stroke: I60.0 - I64.0
Hospital-treated infections (Other than PJI and PJI-likely)	The Danish National Patient Registry (DNPR)	A20 -A38, A42 -A44, A48 -A49, A65 -A79, A3, A49.9, A39.4, A40 -A41, B37.7, A32.7, A54.8G, A02.1, A22.7, A26.7, A42.7, A28.2B, A06.5, A54.1, B43, D73.3, E06.0A, E23.6A, E32.1, G06, G07, H00.0A, H05.0A, H44.0A,

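### PJI-likely does not exclude patients who already have primary PJI, and criterion B links the J01 redemption to the aspirate by neither order nor interval

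*SAP*

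**What the plan says.** The SAP lists PJI-likely as item 2 under "Key secondary endpoints evaluated within 90 days from primary THA". The rule joining its criteria is: "PJI-likely is defined as at least one of the two criteria is fulfilled". Criterion A is a single positive intraoperative culture at reoperation. Criterion B is one positive culture from a synovial aspirate, "regardless of microorganism AND any antibiotic prescriptions (ATC category J01) redeemed". A site restriction applies: "Positive culture samples (aspirations, tissue biopsies or fluid) must be obtained from the relevant hip joint".

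In Appendix B, the PJI-likely row dates the microbiology sample "between 3 and 90 days after a planned index operation". For the prescription it names only the ATC category, with no date. The same row also asks that the culture finding match the organism in a tissue biopsy, a condition that stands in the primary PJI row as well.

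The primary PJI definition (Outcome definitions and endpoints) requires revision within 90 days and any one of three criteria. The third is the surgeon's report of deep infection to the hip register at revision, with no culture requirement.

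Elsewhere the SAP does write exclusions and time windows. Another outcome in Appendix B is labelled "Hospital-treated infections (Other than PJI and PJI-likely", and item 6 looks at "redemption of ATC code J01E prescriptions within one week following the index operation" as a marker of postoperative urinary infection.

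**The concern.** In criterion B the redeemed prescription appears to stand in for a decision to treat the aspirate finding. Without an order or an interval it cannot do that reliably. A patient who redeems an antibiotic for a urinary infection in week 1, and whose hip aspirate in week 10 grows a contaminant that nobody treats, meets criterion B as worded in item 2.

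The second gap is overlap. A patient with a positive aspirate who is revised, meets the PJI definition and then redeems an antibiotic after discharge is counted under PJI and again under PJI-likely. The same happens through criterion A.

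What is at stake is the reading of one key secondary endpoint. A comparison of potential infections that partly repeats the primary endpoint, and partly counts unrelated prescriptions, is hard to interpret in either direction.

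**Working it through.** The SAP states no rate, event count or precision for PJI-likely, so there is no figure to reproduce. The check is a comparison of the texts, followed by an illustration on assumed counts.

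**1. Link between prescription and aspirate.** Item 2 gives no order, interval, indication or agent. The section heading gives an outer limit of 90 days from surgery. The Appendix B window of day 3 to 90 applies to the sample date only. A redemption before the aspirate therefore qualifies.

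**2. Exclusion of primary PJI.** None is written in item 2, in Table 2 or in the Appendix B row. There are two routes to overlap:
- Criterion B: positive aspirate, revision meeting the PJI definition, then a J01 redemption.
- Criterion A: one positive intraoperative culture plus a deep infection reported by the surgeon. This is PJI by its third criterion and PJI-likely by criterion A.

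Reading the single culture as exactly one does not help, because both routes can occur with exactly one positive culture.

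**3. Item 2 against Appendix B.** Item 2 accepts any organism from an aspirate alone. The Appendix B row asks for a match with a tissue biopsy. Read literally, the appendix would reject an aspirate with no biopsy, which is the case criterion B describes. The two texts yield different event lists.

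**4. Illustration.** From the SAP (Sample size and power calculation): up to 10,000 patients per group and a mean PJI rate of 1.2%, so 10,000 × 0.012 = 120 PJI per group. All other inputs are assumptions.

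- Overlap: if 10%, 30% or 60% of the 120 also met criterion B, then 12, 36 or 72 patients per arm would be in both rows.
- Unrelated cases: if 20 to 100 patients per arm had a contaminant aspirate and 10% to 30% of them redeemed J01 for another reason, the range is 20 × 0.10 = 2 to 100 × 0.30 = 30 events per arm.

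Effect on the ratio, taking 50 (multiple-dose) and 70 (single-dose) true PJI-likely events per 10,000, so 70/50 = 1.40. At these rates the odds ratio is almost the same (1.403).

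| Added events (multiple / single) | Ratio |
|---|---|
| none | 70/50 = 1.40 |
| unrelated, 5 / 5 | 75/55 = 1.36 |
| unrelated, 15 / 15 | 85/65 = 1.31 |
| unrelated, 30 / 30 | 100/80 = 1.25 |
| overlapping PJI, 12 / 12 | 82/62 = 1.32 |
| overlapping PJI, 36 / 36 | 106/86 = 1.23 |
| overlapping PJI, 72 / 72 | 142/122 = 1.16 |
| overlapping PJI, 36 / 50.4 | 120.4/86 = 1.40 |

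Unrelated events pull the ratio towards 1 when they are equally frequent in both arms. Overlapping events pull it towards the primary PJI ratio: the rows with equal overlap assume no difference in PJI, and the last row assumes a PJI ratio of 1.40.

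**The case against.** The strongest reply is that this is an unclear secondary definition and little more. Several parts of that stand.

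- A redemption alone never creates an event. A positive culture from the operated hip is always needed, which may keep the number of unrelated cases small.
- The name of the endpoint, and its separate listing beside PJI in Appendix B, suggest a distinct category. That supports the exclusion as the likely intent, but an analyst following the written rule would not apply it.
- Overlap between rows of Table 2 is not an error in itself. A PJI patient also appears under any revision, and no row adds PJI and PJI-likely together.
- A broad any-J01 rule can be a deliberate choice for sensitivity. Requiring the redemption to come after sampling would lose patients treated on suspicion before aspiration.
- The dataset diagram in Appendix A is not visible in the text reviewed, so linkage logic drawn there cannot be ruled out.

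A reader might infer that PJI-likely is the only outcome, or the main check, for infections managed without revision. The SAP does not support this. Serious adverse events, hospital-treated infections, community antibiotic use and rows of Table 3 also capture infections without requiring revision, and the SAP nowhere gives PJI-likely that role. A reader might also infer that overlap always dilutes towards an odds ratio of 1. The last row of the table shows that it need not.

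**Conclusion.** The point holds as a defect in the definition of one key secondary endpoint. As written, PJI-likely counts antibiotics that cannot have been treatment of the aspirate finding, and it repeats primary PJI cases through both criteria. Appendix B also contradicts the main text on which cultures qualify.

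The size cannot be derived from the SAP. The 12 to 72 overlapping patients and 2 to 30 unrelated events per arm rest entirely on assumed shares and show only that the effect could be visible. It would be wrong to conclude that the endpoint mostly repeats primary PJI. The primary endpoint and the non-inferiority conclusion at 1.4 are untouched. The change is worth making before the analysis data are opened, because it is cheap and removes a choice otherwise left to the programmer.

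**What to change.** 1. State that PJI-likely counts only patients who do not meet the primary PJI definition within 90 days, under either criterion. Add a combined row, 'PJI or PJI-likely', to Table 2.
2. In criterion B, tie the J01 redemption to the aspirate's sampling date by a prespecified order and maximum interval. Fourteen days is only an example; the trial team should choose and justify the value. Keep the present any-J01 rule as a sensitivity analysis.
3. Reconcile the PJI-likely row of Appendix B with item 2, so that it is clear whether a tissue-biopsy match is required.

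The cost is a few sentences and a date condition in the linkage. Appendix B already uses the microbiology sample date, and item 6 already relies on redemption timing, so no new data are needed. The downside is that the narrower criterion B misses patients treated only in hospital, those treated on suspicion before aspiration and those who redeem late. For patients with a J01 redemption, the sensitivity analysis shows how much this matters.
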